5.1.6.3 Treatment Interruption or Discontinuation

Atezolizumab treatment may be temporarily suspended in patients experiencing toxicity considered to be related to study treatment. If corticosteroids are initiated for treatment of the toxicity, they must be tapered over \geq 1 month to \leq 10 mg/day oral prednisone or equivalent before atezolizumab can be resumed. If atezolizumab is withheld for $>$ 12 weeks, the patient will be discontinued from atezolizumab. Study treatment may be withheld for $>$ 12 weeks to allow for patients to taper off corticosteroids prior to resuming treatment. Atezolizumab can be resumed after being withheld for 12 weeks if the patient is likely to derive clinical benefit. *The decision to re-challenge patients with atezolizumab should be based on investigator's assessment of benefit-risk and documented by the investigator (or an appropriate delegate). The Medical Monitor is available to advise as needed.* Atezolizumab treatment may be suspended for reasons other than toxicity (e.g., surgical procedures). The acceptable length of treatment interruption *must be based on an assessment of benefit-risk by the investigator and in alignment with the protocol requirements for the duration of treatment and documented by the investigator.* The Medical Monitor is available to advise as needed.

Cobimetinib (Cohort 1) or cobimetinib and vemurafenib (Cohort 2) treatment may be temporarily suspended in patients who experience toxicity considered to be related to

study treatment. If cobimetinib or vemurafenib (if applicable) has been withheld for > 28 days because of toxicity, the patient should be discontinued from that drug, unless *the patient is likely to derive clinical benefit. The decision to re-challenge patients with study treatment should be based on investigator's assessment of benefit-risk and documented by the investigator (or an appropriate delegate)*. The Medical Monitor is available to advise as needed. The Medical Monitor should be consulted for any major surgery (e.g., involving a body cavity), and cobimetinib and vemurafenib (if applicable) should generally be withheld for two days prior to the procedure and for two weeks afterwards.

For dose interruptions required in the run-in period (Cycle 1) in Cohort 2, refer to Section [5.1.6.2](#).

5.1.6.4 Management Guidelines – Cohort 1

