- Resumption of atezolizumab may be considered in patients who are deriving benefit and have fully recovered from the immune-mediated event. *The decision to re-challenge patients with atezolizumab should be based on investigator's assessment of benefit–risk and documented by the investigator (or an appropriate delegate)*. *The Medical Monitor is available to advise as needed*.

Appendix 12: Guidelines for Management of Patients Who Experience Specific Adverse Events in Cohort 1

Table 3: Dermatologic Toxicity

Dermatologic toxicity	
Event	Action to be taken
General guidance	
 A dermatologist should evaluate persistent and/or severe rash or pruritus. A biopsy should be considered unless contraindicated.
Dermatologic event, Grade 1 or 2	
 Continue atezolizumab and cobimetinib. Initiate supportive care (e.g., antihistamines, topical corticosteroids). If event does not improve, consider treatment with higher-potency topical corticosteroids. For Grade 2, if unresponsive to topical corticosteroids, consider oral prednisone 0.5 mg/kg/day. For Grade 2 rash, consider referral to dermatologist. 
Acneiform rash:
 
 Consider topical corticosteroids (e.g., hydrocortisone 2.5%, alclometasone) and oral antibiotics (minocycline, doxycycline, or antibiotics covering skin flora) as clinically indicated.
Dermatologic event, Grade 3	
 Withhold atezolizumab and cobimetinib. Refer patient to dermatologist. A biopsy should be performed if appropriate. Consider initiating treatment with 10 mg/day oral prednisone or equivalent, increasing dose to 1–2 mg/kg/day if event does not improve within 48–72 hours. If event resolves to Grade 2 or better within 12 weeks, resume atezolizumab at fixed dose. If not, permanently discontinue atezolizumab and cobimetinib. [a, b] Permanently discontinue atezolizumab and cobimetinib and contact Medical Monitor if event does not resolve to Grade 1 or better within 12 weeks. [a, b, c] If event resolves to Grade 2 or better within 28 days, resume cobimetinib with dose reduced by one level. If not, permanently discontinue cobimetinib. 
Acneiform rash:
 
 Consider continuation of topical corticosteroids (e.g., 2.5% alclometasone) and oral antibiotics (e.g., minocycline, doxycycline or antibiotics covering skin flora) when restarting cobimetinib.

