Dermatologic event, Grade 4	
 Permanently discontinue atezolizumab and cobimetinib, and contact Medical Monitor. [c]
Stevens-Johnson syndrome or toxic epidermal necrolysis (any grade)	
Additional guidance for Stevens-Johnson syndrome or toxic epidermal necrolysis:
 
 Withhold atezolizumab for suspected Stevens-Johnson syndrome or toxic epidermal necrolysis.

Appendix 12: Guidelines for Management of Patients Who Experience Specific Adverse Events in Cohort 1

Dermatologic toxicity	
Event	Action to be taken
	
• Confirm diagnosis by referring patient to a specialist (dermatologist, ophthalmologist, or urologist as relevant) for evaluation and, if indicated, biopsy.• Follow the applicable treatment and management guidelines above.• If Steven-Johnson syndrome or toxic epidermal necrolysis is confirmed, permanently discontinue atezolizumab.

- a. If corticosteroids have been initiated, they must be tapered over \geq 1 month to \leq 10 mg/day oral prednisone or equivalent before atezolizumab can be resumed.
- b. Atezolizumab may be withheld for a period of time beyond 12 weeks to allow for corticosteroids to be reduced to \leq 10 mg/day oral prednisone or equivalent. The acceptable length of the extended period of time must be *based on an assessment of benefit–risk by the investigator and in alignment with the protocol requirements for the duration of treatment and documented by the investigator. The Medical Monitor is available to advise as needed.*
- c. Resumption of atezolizumab may be considered in patients who are deriving benefit and have fully recovered from the immune-mediated event. *The decision to re-challeng patients with atezolizumab should be based on investigator's assessment of benefit-risk and documented by the investigator (or an appropriate delegate). The Medical Monitor is available to advise as needed.*

Appendix 12: Guidelines for Management of Patients Who Experience Specific Adverse Events in Cohort 1

Table 4: Elevated Liver Enzymes

Elevated liver enzymes	
Event	Action to be taken
AST/ALT > ULN to $\leq 3 \times$ ULN with total bilirubin $< 2 \times$ ULN	
 Continue atezolizumab and cobimetinib. Continue with the standard monitoring plan (i.e., LFTs Q4W before dosing).

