Although most immune-mediated adverse events observed with immunomodulatory agents have been mild and self-limiting, such events should be recognized early and treated promptly to avoid potential major complications. Discontinuation of atezolizumab may not have an immediate therapeutic effect, and in severe cases, immune-mediated toxicities may require acute management with topical corticosteroids, systemic corticosteroids, or other immunosuppressive agents.

The investigator should consider the benefit–risk balance a given patient may be experiencing prior to further administration of atezolizumab. In patients who have met the criteria for permanent discontinuation, resumption of atezolizumab may be considered if the patient is deriving benefit and has fully recovered from the immune-mediated event. *The decision to re-challenge patients with atezolizumab should be based on investigator's assessment of benefit–risk and documented by the investigator (or an appropriate delegate). The Medical Monitor is available to advise as needed.*

DOSE MODIFICATIONS

There will be no dose modifications for atezolizumab in this study.

TREATMENT INTERRUPTION

Atezolizumab treatment may be temporarily suspended in patients experiencing toxicity considered to be related to study treatment. If corticosteroids are initiated for treatment of the toxicity, they must be tapered over ≥ 1 month to ≤ 10 mg/day oral prednisone or equivalent before atezolizumab can be resumed. If atezolizumab is withheld for > 12 weeks after event onset, the patient will be discontinued from atezolizumab. However, atezolizumab may be withheld for > 12 weeks to allow for patients to taper off corticosteroids prior to resuming treatment. Atezolizumab can be resumed after being withheld for > 12 weeks if the patient is likely to derive clinical benefit. *The decision to re-challenge patients with atezolizumab should be based on investigator's assessment of benefit–risk and documented by the investigator (or an appropriate delegate). The Medical Monitor is available to advise as needed. Atezolizumab treatment may be suspended for reasons other than toxicity (e.g., surgical procedures). The acceptable length of treatment interruption must be based on an assessment of benefit–risk by the investigator and in alignment with the protocol requirements for the duration of*

Appendix 14:Risks Associated with Atezolizumab and Guidelines for Management of Adverse Events Associated with Atezolizumab

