Dermatologic event, Grade 3	
 Withhold atezolizumab for up to 12 weeks after event onset [a]. Refer patient to dermatologist for evaluation and, if indicated, biopsy. Initiate treatment with 10 mg/day oral prednisone or equivalent, increasing dose to 1–2 mg/kg/day if event does not improve within 48–72 hours. If event resolves to Grade 1 or better, resume atezolizumab [b]. If event does not resolve to Grade 1 or better while withholding atezolizumab, permanently discontinue atezolizumab and contact Medical Monitor [c].
Dermatologic event, Grade 4	
 Permanently discontinue atezolizumab and contact Medical Monitor [c].
Stevens-Johnson syndrome or toxic epidermal necrolysis (any grade)	
Additional guidance for Stevens-Johnson syndrome or toxic epidermal necrolysis:
 
 Withhold atezolizumab for suspected Stevens-Johnson syndrome or toxic epidermal necrolysis. Confirm diagnosis by referring patient to a specialist (dermatologist, ophthalmologist, or urologist as relevant) for evaluation and, if indicated, biopsy. Follow the applicable treatment and management guidelines above. 
If Stevens-Johnson syndrome or toxic epidermal necrolysis is confirmed, permanently discontinue atezolizumab.

- Atezolizumab may be withheld for a longer period of time (i.e., > 12 weeks after event onset) to allow for corticosteroids to be reduced to \leq 10 mg/day oral prednisone or equivalent. The acceptable length of the extended period of time must be based on an assessment of benefit–risk by the investigator and in alignment with the protocol requirements for the duration of treatment and documented by the investigator. The Medical Monitor is available to advise as needed.
- If corticosteroids have been initiated, they must be tapered over \geq 1 month to \leq 10 mg/day oral prednisone or equivalent before atezolizumab can be resumed.
- Resumption of atezolizumab may be considered in patients who are deriving benefit and have fully recovered from the immune-mediated event. The decision to re-challenge patients with atezolizumab should be based on investigator's assessment of benefit–risk and documented by the investigator (or an appropriate delegate). The Medical Monitor is available to advise as needed.

NEUROLOGIC DISORDERS

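### Cohort 1, Grade 3 skin event (Protocol Appendix 12, Table 3): for an event at Grade 2 at week 12, one bullet resumes atezolizumab and the next permanently stops it

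*Protocol*

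**What the plan says.** The Grade 3 row of Appendix 12, Table 3 (Dermatologic Toxicity, Cohort 1) withholds both drugs, refers the patient to a dermatologist, and then gives three rules on restarting or stopping.

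- Atezolizumab, resume rule: "If event resolves to Grade 2 or better within 12 weeks, resume atezolizumab at fixed dose". Its failure branch stops both drugs permanently.
- Both drugs, stop rule: "Permanently discontinue atezolizumab and cobimetinib and contact Medical Monitor if event does not resolve to Grade 1 or better within 12 weeks".
- Cobimetinib, 28-day rule: "If event resolves to Grade 2 or better within 28 days, resume cobimetinib with dose reduced by one level". Its failure branch stops cobimetinib permanently.

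The row above, for Grade 1 or 2 events, says: "Continue atezolizumab and cobimetinib. Initiate supportive care (e.g., antihistamines, topical corticosteroids".

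Four other places bear on the choice.

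- Table 3, footnotes a and b cover steroid taper and longer withholding. Footnote c says: "Resumption of atezolizumab may be considered in patients who are deriving benefit and have fully recovered from the immune-mediated event".
- Section 5.1.6.3, and the general guidance in Appendix 12, Table 1, say: "Atezolizumab can be resumed after being withheld for 12 weeks if the patient is likely to derive clinical benefit". This rests on the investigator's documented benefit-risk assessment.
- The introduction to Appendix 14 says that, after the criteria for permanent discontinuation are met, "resumption of atezolizumab may be considered if the patient is deriving benefit and has fully recovered from the immune-mediated event".
- Appendix 14, Table 9, to which Section 5.1.6.1 also directs Cohort 1, resumes atezolizumab after a Grade 3 skin event only at Grade 1 or lower, and adds: "If event does not resolve to Grade 1 or better while withholding atezolizumab, permanently discontinue atezolizumab and contact Medical Monitor".

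Section 4.2 closes Cohort 1 to new patients but lets ongoing patients stay on treatment.

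**The concern.** The resume rule and the stop rule share a clock (12 weeks) and a drug (atezolizumab) but use different grades. A patient whose severe skin event has improved to Grade 2 but no further meets the condition of both. Two sites reading the same cell could take opposite default actions on a checkpoint inhibitor after a severe skin reaction, and each could point to the text.

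Cobimetinib has a related problem. The 28-day rule restarts it at Grade 2, and the stop rule ends it permanently if the event is still at Grade 2 at week 12. The table does not say how the two fit together.

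What is at stake is consistent treatment of individual patients, not the trial's inference.

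**Working it through.** No sample size, power or event count is involved, so the check sets the rules side by side and takes each possible state of the event at week 12 in turn.

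| Event at week 12 | Resume rule | Stop rule | Agree? |
|---|---|---|---|
| Grade 1 or lower | Resume atezolizumab | Not triggered | Yes |
| Grade 2 | Resume atezolizumab | Permanently stop both drugs | No |
| Grade 3 or higher | Permanently stop both drugs | Permanently stop both drugs | Yes |

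The conflict is confined to Grade 2.

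**Can other text resolve it?**

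1. Footnotes a and b concern steroids and the length of withholding. Neither sets a grade.
2. Footnote c and the Appendix 14 introduction require full recovery. An event still at Grade 2 has not fully recovered.
3. Section 5.1.6.3 and the Appendix 12 general guidance permit an exception. They do not state the rule to which it is an exception.
4. Appendix 14, Table 9 uses Grade 1, which agrees with the stop rule. No text says that Appendix 14 overrides Appendix 12; Section 5.1.6.1 calls it additional guidance.
5. Grade 2 also has support: the Grade 1 or 2 row continues both drugs, the cobimetinib rule uses Grade 2, and Appendix 13 uses Grade 2 for acneiform rash in Cohort 2.

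The intended threshold therefore cannot be read off the documents.

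**Comparison within Appendix 12.** The diarrhoea and colitis rows (Table 2) and the Grade 2 pneumonitis row (Table 5) also have a 12-week resume-or-stop rule. Each uses Grade 1 for both branches. The Grade 3 skin row does not.

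**Cobimetinib.** Suppose the event reaches Grade 2 by day 28 and stays there. The 28-day rule restarts cobimetinib one dose level down. At week 12 the stop rule ends it permanently, while the failure branch of the resume rule is not triggered and leaves it running. The cell does not say which applies.

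**Reach.** Section 6.1 gives 15 patients enrolled in Cohort 1 as of 9 July 2019. The number still on treatment is not stated, so 15 is an upper bound.

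**The case against.** The strongest reply is that the rules work in sequence: restart atezolizumab when the event reaches Grade 2, then stop at week 12, with Medical Monitor contact, if Grade 1 has not followed. This reading is possible, and a redundant failure branch in the resume rule would not by itself be a contradiction. But the sequence is not written. It also fails for an event that first reaches Grade 2 at week 12, which would be told to resume and to stop at once.

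A second reply is that Appendix 12 is guidance and that Section 5.1.6.3 leaves room for judgement, so either action at week 12 can be compliant. That stands, and it limits the harm. So do the dermatologist referral and the separate rule for Stevens-Johnson syndrome and toxic epidermal necrolysis. Discretion to depart from a default still needs a stated default.

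A reader might infer more than the documents support.

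- **That the Grade 2 bullet is simply an error.** Appendix 14 favours Grade 1, but the passages listed above favour Grade 2, and nothing ranks them.
- **That the Cohort 2 rash rules in Appendix 13 are faulty in the same way.** They differ from Appendix 14, but no contradiction within that table has been shown. Cohort 2 adds vemurafenib, and Section 5.1.6.5 directs interruptions to the drug judged the main cause.
- **That the number of affected patients can be estimated by applying an earlier rash rate to all 15.** Enrolment closed in July 2019, so this would count mostly past exposure, and the share of such events at Grade 2 at week 12 is not given.

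**Conclusion.** The contradiction is real and lies within one table cell: an event at Grade 2 at week 12 has two opposite default instructions for atezolizumab, and the documents do not say which governs. The 28-day cobimetinib rule and the 12-week stop are also unreconciled.

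The severity is minor. The point can affect only Cohort 1 patients who are still on treatment and have a Grade 3 skin event that settles at Grade 2. It would be wrong to infer that trial results are at risk: SAP Section 5.1 does not evaluate the primary endpoint in Cohort 1, and no sample size, endpoint or analysis depends on this rule. The conclusion rests on the wording of the table and the cross-references above, and on no numerical assumption.

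**What to change.** The sponsor should confirm the threshold and replace the two 12-week bullets with one. Unless Grade 2 is confirmed, use the Grade 1 threshold of Appendix 14, Table 9: restart atezolizumab at the fixed dose if the event is at Grade 1 or lower within 12 weeks; otherwise stop atezolizumab permanently and contact the Medical Monitor. Keep footnotes a, b and c.

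In the same cell, settle cobimetinib in one of two ways:

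- let the 28-day bullet alone govern it; or
- state explicitly that cobimetinib restarted at Grade 2 is stopped if the event is not at Grade 1 at week 12.

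The first option is simpler but lets cobimetinib continue after atezolizumab stops, unlike the diarrhoea, colitis and pneumonitis rows, whose 12-week failure stops both drugs. The second keeps that pattern.

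The cost is a change of dosing wording by amendment. Under Section 9.7 this needs IRB/EC approval and, where locally required, regulatory approval. The clinical downside of Grade 1 is that a patient whose skin event persists at Grade 2 stops atezolizumab by default, and one who reaches Grade 2 early waits for Grade 1 before restarting. Both remain subject to the investigator's documented benefit-risk discretion.

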## **STATISTICAL ANALYSIS PLAN VERSION HISTORY**

This statistical analysis plan (SAP) was developed based on Roche SAP model document updated on 26 October 2020.

SAP Version	Approval Date	Based on Protocol (Version, Approval Date)
2.0	see electronic date stamp on title page  day month year	Version 4.0, 26 February 2020
1.0	17 April 2019	Version 2.0, 6 November 2018

## **STATISTICAL ANALYSIS PLAN AMENDMENT RATIONALE**

Key changes to the SAP, along with the rationales for each change, are summarized below.

Section	Description of Change	Rationale for Change
4	Patient-reported outcome (PRO)-evaluable population added for the PRO analysis	It is stated in the protocol that “Only patients with a non-missing baseline assessment and at least one non-missing post-baseline assessment will be included in PRO analyses.” For clarify purpose, we added PRO population in the Section 4 and clarified that this population will be used for PRO analysis to ensure compliance with the protocol.
5.1	Only a subset of efficacy analysis will be done on Cohort 1	Given that the recruitment of Cohort 1 was stopped prematurely, it is no longer appropriate to produce all the efficacy analysis due to small sample size. Thus, the Statistical Analysis Plan is updated to limit the efficacy analysis.
5.3.1	No analysis on primary endpoint on Cohort 1	After the premature discontinuation of Cohort 1, it was decided to not perform the independent review of scan for patients in Cohort 1. Thus, all analyses on the primary endpoint will be performed on Cohort 2 only.
5.3.3	Adding sensitivity analysis of primary endpoints on all treated patients (safety population)	The analysis on primary endpoint is planned on evaluable population only, which excludes subjects with less than 2 scans. Excluding these subjects could lead to an inflation of the response rate by excluding the early progression or death. Therefore, we add an analysis on all treated patients to assess the bias introduced by excluding these patients.
5.3.4.1	New subgroup	Additional subgroup added to better explore the effect of demographic characteristics and clinical and biological prognostic factors on the efficacy endpoint.
5.4	Adding analysis secondary efficacy endpoints on all treated patients (safety population)	The analysis on efficacy endpoint (objective response rate [ORR], progression-free survival [PFS], and disease control rate [DCR]) are planned on evaluable population, which excludes subjects with less than 2 scans. Excluding these subjects could lead to an inflation of the response rate by excluding the early progression or death. Therefore, we add an analysis on all treated patients to assess the bias introduced by excluding these patients.
5.4.2.8	Update the definition of time to deterioration (TTD) to a decrease of 10 point from baseline for functional scale TTD will be performed on each scale separately	A high score on functional scale and a low score on symptom scale is an improvement as per the scoring manual. Thus, a deterioration for functioning scale and Global Health Status (GHS)/ Quality-of-Life (QoL) for Core 30 (QLQ-C30) is defined by a decrease of 10 point from baseline. A deterioration for symptoms scale for QLQ-C30 and items for Quality-of-Life Questionnaire brain cancer module (QLQ-BN20) is defined by an increase of 10 point from baseline.

		Each scale measure different functions and symptoms. Thus, it is more meaningful to evaluate the TTD on each symptom and function separately.
5.5.1.6	Add analysis on change in corticosteroid use	New analyses are added to explore the change in corticosteroid use based on data collected case report form (CRF).
5.5.1.8	Add PFS, duration of response (DoR) and DCR by independent review committee (IRC)	To assess the bias introduced on efficacy endpoint as determined by investigator using response evaluation criteria in solid tumors (RECIST).
5.6	Safety analysis will be done separately for patients in Cohort 2 who actually received and didn't receive the triplet combination during the treatment period	To evaluate safety on patients who actually received the triplet combination and those who received only cobimetinib and vemurafenib. Patients in Cohort 2 will receive cobimetinib and vemurafenib during the run-in period (Cycle 1) and with the triplet combination (cobimetinib, atezolizumab, and vemurafenib) post run-in (Cycle 2 onwards).
6.2	Replaced analysis of adverse events (AEs) by highest grade by analysis of AE by System Organ Class (SOC) and Preferred Term (PT)	Summary of some AEs (such as AE leading to study drug discontinuation, etc.) by highest grade are removed when not appropriate. They are replaced by a summary of the incidence by SOC and PT only.
5.6.2	Add a list of suspected Coronavirus Disease (COVID) case	To identify potential COVID case in the study, if any.
5.6.2	Add analysis on AE during run-in and post run-in in Cohort 2	To evaluate safety during triple combination period and during the period where only cobimetinib and vemurafenib are administered.
5.7.1	Add summary of pharmacodynamic related to COVID	To assess potential impact of COVID.

Additional minor changes have been made throughout to improve clarity and consistency.

